5. STUDY DESIGN

5.1. Overview

The study is designed to observe the clinical outcomes of heart failure patients treated with the C-Pulse® System in the usual manner and according to the approved indications and contraindications.

A maximum of 15 European sites will participate. Study data from additional geographies may be included

The study will include a cohort of up to 50 patients with moderate to severe heart failure refractory to optimal medical therapy, who receive the C-Pulse® System at the study sites. Patients must have provided written consent that their data can be used in the study. The patients will be followed for up to 5 years to collect performance and safety data. All available follow-up data of patients treated with the study device at the participating sites will be recorded via electronic CRFs.

The study will have the following estimated time course:

First Patient In: May 2013

Last Patient In: Dec 2014

Last Patient Out: Dec 2019

5.2. Inclusion Criteria

The inclusion criteria are consistent with the indications section of the C-Pulse® System Instruction For Use (IFU). According to the CE mark authorization, patients with the following conditions can be included:

1. Patient is 18 years or older
2. Patients with moderate to severe heart failure [American College of Cardiology/American Heart Association (ACC/AHA) Stage C; NYHA Class III/IV ambulatory], who are refractory to optimal medical therapy.
3. Patients who are non-responders to CRT pacemaker therapy. When clinically indicated, CRT should be implanted ≥ 90 days prior to enrollment.

In addition:

4. Patient has signed and dated the investigation informed consent form.

As the C-pulse implantation procedure is clinically indicated patients may be enrolled prospectively with informed consent obtained prior to the procedure or retrospectively with informed consent for the collection of the patient's data obtained after the procedure as appropriate for an observational study.

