5.4. Patient Recruitment

Patient authorization and written informed consent must be obtained prior to the patient's enrollment into the study and in accordance with GCPs, the Medical Devices Directive and all other applicable standards, regulations (local and national), guidelines and institutional policies.

The investigator(s) will verify each patient's inclusion/exclusion criteria before inclusion in the study. Selection criteria and completion of informed consent will be indicated on the Case Report Form.

All patients who sign a consent form will be assigned a study identification number. The identification number will be formatted using the abbreviation for the country, site identification number – sequential site recruited patient number (i.e. DE-005-004). Any patient meeting the study inclusion criteria, for whom this device is clinically indicated, can be recruited for the study after receiving and documenting informed consent.

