5.6. Schedule of Assessments

The study will aim to collect patient data while supported with C-Pulse therapy (i.e. the subjects will be censored from analysis if the device is permanently "off"). Data will be captured at the following time points: Baseline, procedure, discharge assessment, clinical follow-up at 6 weeks, 6 months, 12 months, 18 months, 2 years and yearly thereafter. Data from any other additional time points may be collected and analyzed if available.

The treatment procedure will be performed according to the instructions outlined in the current approved IFU. The data will be recorded from baseline and during a 5 year follow-up period following the enrollment. Treatments will be performed according to standard hospital practices. The clinical assessments will be done as per routine practice at the participating institutions.

The clinical variables of interest are presented in **Table 8** below. Hemodynamic performance and functional testing will be determined according to procedures based on standard center practices. Any protocol-defined adverse events, including adverse device effects and outcomes will be reported by the Investigator. All available variables of interest, that will be collected by the investigators, will also be recorded in the Study electronic CRFs.

Table 3 .Data Collection Summary.

	Pre-Implant (Baseline)	Implant	Pre-Discharge ²	6 week	6, 18 month	Annually ¹ Yr 1-5
PATIENT ELIGIBILITY	X					
GENERAL						
Demographic Data	X					
Medical History	X					
General Physical Exam	X	X	X	X	X	X
Concurrent Cardiac Meds	X	X	X	X	X	X
Weight (Height at enrollment)	X		X	X	X	X
Pregnancy test (if applicable)	X					
VITAL PARAMETERS						
Heart rate/rhythm	X		X	X	X	X
Blood pressure	X		X	X	X	X
Respiration rate	X		X	X	X	X
CARDIOPULMONARY³						
ECHO	X				X	X
6MWT	X			X	X	X
QUALITY OF LIFE						
INTERMACS™/NYHA Classification	X			X	X	X
KCCQ	X				X	X
HEMATOLOGY						
Hemoglobin	X		X		X	X
Hematocrit	X		X		X	X
Platelet count	X		X		X	X
White cell count	X		X		X	X
C-reactive Protein	X		X		X	X
BIOCHEMISTRY						
Serum sodium	X		X		X	X
Serum potassium	X		X		X	X
Serum creatinine	X		X		X	X
BUN	X		X		X	X
NTProBNP or BNP ⁴	X				X	X
Serum bilirubin	X		X		X	X
Serum ALT	X		X		X	X
Serum AST/GGT	X		X		X	X
IMPLANT DETAILS		X				
DEVICE LOG		X			X	X
DISCHARGE CHECKLIST			X			
ADVERSE EVENTS	X	X	X	X	X	X
DATA FROM THE FOLLOWING ITEMS WILL BE COLLECTED IF COMPLETED UPON PHYSICIAN REQUEST:						
MVO2	X					X
Right Heart Catheterization	X					X

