6.5. Statistical Methodology

The sample size for the European protocol (N= 50 patients) was calculated on the basis of preliminary discussions with the Scientific Advisors of Sunshine Heart, and predicted success and safety rates observed in the literature data. Consistent design, procedures and endpoints of this study, as compared with the US trial, may allow pooling of data and comparative analyses. Demographic and baseline data will be summarized using descriptive statistics, including %, mean, median, standard deviation, and 1st-3rd quartile, as appropriate. The performance and safety endpoints of the C-Pulse® System will be assessed by monitoring the patient clinical status, assessing the standard quality-of-life scores, and evaluating vital, cardiopulmonary, hematology, biochemistry and neurological parameters, cardiopulmonary test data during the visits within the follow-up period, as detailed in the Data Collection Summary shown in Table 8. Follow-up analysis will include both safety and performance analyses, at each of the defined intervals. Adverse event data will be summarized using descriptive statistics. These will include information concerning nature, severity and duration of all adverse events and their relationship to the different treatments. In addition, tables will be presented for the number of patients potentially available for follow-up and those actually followed. Reference rates for anticipated complications (adverse events), based on historical data on morbidity and mortality from previous device clinical experience, in similar populations and for analogous surgical procedures, are listed in the Literature Review. Overall mortality rate will be determined at the end of the study.

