7.2. Information Collected in the Electronic Case Report Forms (e-CRFs)

The study physician or his designee at each clinical site will perform primary data collection. Only the study physician or other pre-designated study personnel will be authorized to enter data (from source documents) via internet-based e-CRFs. Study personnel will each be assigned a unique user name and pass code to access the e-CRFs. Representatives, agents or consultants of the Data Management Center, the Sponsor or other designee will provide training, clinical monitoring, including review of e-CRFs with verification to the source documentation.

Study patients will be enrolled based on the current approved labeling (as outlined in the Instructions for Use). Eligibility for each patient enrolled will be based on the current CE mark labeling and will be documented appropriately in the medical records (source documents) and entered in the e-CRFs.

Only anonymous data will be collected after the patient has consented that personal data can be used. Patients treated with the study device are asked to consent in writing that their data can be entered into a central database.

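### Patients enrolled after implant must have survived to sign consent, so early mortality may be understated; the plan neither reports them separately nor allows for delayed entry

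*Combined protocol and SAP*

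**What the plan says.** **Entry.** The combined protocol and SAP allows consent before or after implant in three places: the synopsis (Screening process), section 4.1 and section 5.2. The last admits patients "retrospectively with informed consent for the collection of the patient's data obtained after the procedure as appropriate for an observational study". No cap on the number of such patients and no limit on the delay to consent is given.

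**Condition for data to count.** Four sections make the patient's own agreement the way in:
- Section 5.1: "Patients must have provided written consent that their data can be used in the study".
- Section 5.2, criterion 4: "Patient has signed and dated the investigation informed consent form".
- Section 5.4: "Patient authorization and written informed consent must be obtained prior to the patient's enrollment into the study".
- Section 7.2: "Only anonymous data will be collected after the patient has consented that personal data can be used".

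**Analysis.** Mortality, all-cause and device-related, is among the primary safety endpoints in section 6.4. Section 6.5 states: "Follow-up analysis will include both safety and performance analyses, at each of the defined intervals". It adds: "Overall mortality rate will be determined at the end of the study". The data collection points in section 5.6 are "Baseline, procedure, discharge assessment, clinical follow-up at 6 weeks, 6 months, 12 months, 18 months, 2 years and yearly thereafter". Section 6.5 does not distinguish patients by when they consented, and it names no survival method or time origin.

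**The concern.** A patient who enters after implant cannot, by construction, have died between implant and signature. If that patient is then counted from the procedure onward, the interval before consent adds a survivor to the denominator with no chance of adding a death. This is left truncation, or immortal time. It falls on the procedure, discharge and 6-week intervals, where surgical deaths would appear.

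Section 4.1 gives one purpose of the study as confirming favorable premarket results. An unseen loss of early deaths would lean towards the device on a primary safety endpoint, and a confidence interval would not reveal it. The concern covers mortality and fatal complications. No direction is claimed for non-fatal events.

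**Working it through.** **The plan's own figures.** There is no stated mortality rate to reproduce. Section 6.6 gives N = 50 with two-sided 95% intervals. Its supporting table is not in the text available, which is not counted as an error. For scale, exact (Clopper-Pearson) intervals at N = 50 are 0 to 7.1% for 0/50, 0.5% to 13.7% for 2/50 and 10.0% to 33.7% for 10/50.

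**Inputs, all assumed, because the documents give none.**
- m: true early mortality, equal in both groups.
- f: share of implants approached only after implant.
- q: share of early deaths in that group that precede consent.
- Everyone else consents.

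**Early mortality as seen.** Deaths seen divided by patients seen gives m(1 − fq)/(1 − mfq). For m = 5%:

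| f | q = 1 | q = 0.5 | q = 0.25 |
|---|---|---|---|
| 10% | 4.5% | 4.8% | 4.9% |
| 30% | 3.6% | 4.3% | 4.6% |
| 50% | 2.6% | 3.8% | 4.4% |

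Example, f = 0.3 and q = 1: 0.05 × 0.70/(1 − 0.015) = 0.035/0.985 = 3.6%.

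**Unseen deaths per 50 implants:** 50 × f × m × q. At f = 0.3 this is 0.75, 0.375 and 0.19 for q = 1, 0.5 and 0.25. It exceeds one only at f = 0.5, q = 1 (1.25).

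**In whole counts.** Two deaths among 50 enrolled is 4.0% (0.5% to 13.7%). Two further deaths before consent would make 4/52 = 7.7% (2.1% to 18.5%). The intervals overlap widely.

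**Direction is not fixed.** Take f = 0.5, early mortality of 8% in the prospective group and 2% in the retrospective group (true overall 5.0%), and all retrospective early deaths before consent. If only 20% of retrospective survivors consent, the rate seen is 0.5 × 0.08/(0.5 + 0.5 × 0.98 × 0.2) = 0.040/0.598 = 6.7%, an overstatement. If all survivors consent it is 0.040/0.990 = 4.0%.

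**Later mortality.** With S the survival function and L the lag to consent, the rate seen at time T is [(1 − f)(1 − S(T)) + f(S(L) − S(T))]/[(1 − f) + f·S(L)]. Assume 20% mortality at 12 months, constant hazard and a 90-day lag. For f = 10%, 30% and 50% the rate seen is 19.6%, 18.7% and 17.8% at 12 months. At 5 years a true 67.2% (1 − 0.8⁵) is seen as 67.1%, 66.7% and 66.3%.

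The 12-month result depends on the hazard shape. Constant hazard implies only 2.5% dead by 6 weeks. At f = 0.5, if instead 5% die by 6 weeks, all retrospective deaths in that period precede consent and 12-month mortality is still 20%, the rate seen is (0.5 × 0.20 + 0.5 × 0.15)/(0.5 + 0.5 × 0.95) = 0.175/0.975 = 17.9%. Constant hazard with the same 6-week lag gives 19.0%.

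**Would a prospective-only early rate be better?** Compare root-mean-square error with 50 enrolled and m = 5%. For the pooled rate p it is √[(p − m)² + p(1 − p)/50]. For the prospective subset it is √[m(1 − m)/n], with n the expected prospective patients among the 50.
- f = 0.5, q = 1: pooled √(2.44² + 2.23²) = 3.3 points; prospective-only, n = 25.6, 4.3 points.
- f = 0.3, q = 0.5: pooled 3.0 points; prospective-only, n = 35.3, 3.7 points.

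The pooled rate has the smaller error in all nine cells of the table.

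**Delayed entry.** In simulations of 50 enrolled with the 20%, 90-day example, delayed entry gave 19.9% (SD 5.8 points) against 18.6% (SD 5.4) for the unadjusted analysis at f = 0.3. At f = 0.5 it gave 20.0% (SD 6.2) against 17.9% (SD 5.4). The bias goes and the spread grows.

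**The case against.** - **The route may hardly be used.** Section 6.1 calls the study prospective, and sections 5.5 and 6.2 have suitability agreed between investigator and sponsor, which suggests that most candidates are known before implant. This stands, and it is why the size may be near zero. The route is nevertheless expressly permitted without limit.
- **The plan already captures or counts these patients.** Section 5.1 speaks of recording all available follow-up on treated patients, and section 6.5 promises tables of patients available and patients followed. The first comes directly after the consent requirement. The second is not described as covering implanted patients who never consented. Provision for deaths before signing may lie in removed consent pages or in the local rules to which section 5.4 refers, so absence can be stated only for the visible text.
- **A split by entry type proves nothing alone.** This is correct. Few early deaths among retrospective patients could mean that deaths were lost or that none occurred. Only a count of all implants, with deaths before consent, can tell these apart.
- **The unbiased alternatives are noisier.** This is also correct. At these sample sizes the prospective-only early rate has the larger total error, and delayed entry is unbiased only if consent timing is unrelated to risk of death. Both belong beside the pooled estimate as sensitivity analyses.

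**Conclusion.** The concern holds conditionally. The plan permits entry after implant, requires the patient's own consent before data count, and pools mortality without separating these patients. If some patients are approached only after implant and some die before signing, and if risk and survivors' consent are similar in both groups, early mortality and fatal complications are understated. At an assumed true rate of 5% and a 30% retrospective share, 3.6% to 4.6% would be seen, or under one unseen death per 50 implants.

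A reader might infer that the study's early mortality will certainly be too low, or that the prospective patients alone should supply it. The documents support neither. They give no retrospective share, consent delay or early mortality. The bias is zero if the route is unused or nobody dies before signing, and it can reverse if the groups differ. The effect on 12-month and 5-year mortality is small in most of the cases examined, though the 12-month figure depends on how early the deaths fall.

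Rating: a modest reporting and analysis improvement, with moderate confidence.

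**What to change.** 1. Keep the pooled estimate. Beside it, report mortality and the other safety endpoints at procedure, discharge and 6 weeks by entry type (consented before or after implant), with exact 95% intervals. Label the prospective-only early rate as a sensitivity estimate.
2. Add a sensitivity time-to-event analysis of mortality with implant as time zero and retrospective patients entering the risk set at consent. State that it assumes consent timing is unrelated to risk of death and needs enough prospective patients at risk from day 0.
3. Make implant date and consent date required e-CRF fields. Section 7.4 lists the date of study entry and the procedure date only among items that source documents may contain.
4. Where ethics and data rules permit, report for each site an aggregate count of all implants, of patients never consented and of deaths before consent.
5. Reconcile the five-year clock, which runs from enrollment in section 5.6 and from implantation in section 6.2, and the two consent timings in the synopsis (before screening procedures, or after the procedure).

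**Cost.** Two required dates, one aggregate count per site and one added survival analysis in a plan that is otherwise descriptive. Subgroup intervals are wider: with zero events the upper limit, 1 − 0.025^(1/n), is 7.1% at n = 50, 10.0% at n = 35 and 13.7% at n = 25. Recruitment and care do not change.

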5.3. Exclusion Criteria

Patients with the following conditions (contraindications in the IFU), as assessed within 90 days prior to enrollment, have to be excluded:

1. Evidence of significant ascending aortic calcification on postero-anterior chest X-ray or CT scan

2. Moderate or severe atherosclerotic aortic disease
3. Ascending aorto-coronary artery bypass grafts
4. Any history of aortic dissection
5. Connective tissue disorder such as Marfans disease
6. Previous aortic root replacement
7. Aorta not conforming to specified dimensional constraints
8. Patient has severe mitral valve incompetence, grade 4+
9. Patient has moderate to severe aortic valve incompetence, grade 2 - 4+
10. Patient has systolic blood pressure less than 90 or greater than 140mmHg
11. Presence of active systemic infection
12. Presence of bleeding or coagulation disorder (relative)

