6.2. Enrollment

A patient population of up to 50 patients with moderate to severe heart failure refractory to optimal medical therapy, who are implanted with the C-Pulse System as clinically appropriate, will be enrolled into the Study. A maximum of 15 European centers will participate. Study data from additional geographies may be included.

Patients diagnosed with moderate to severe heart failure and who are treated at the participating centers are eligible for screening evaluation. The investigator(s) will obtain informed consent for study participation from each patient.

Patients eligible for the study must meet all the inclusion criteria and not meet the exclusion criteria (indications and contraindications based on device CE mark authorization and Instructions for Use). In addition, a screening process will be carried out the objective of selecting ideal candidates for the C-Pulse System (see Section 5.5). Patients suitability will be evaluated in agreement between the Investigator and Sponsor, based on the assessment of heart failure severity, concomitant cardiac disease, need for concomitant cardiac surgery, co-morbidity, life expectancy < 2 years, pregnancy and other conditions potentially interfering with the ability to manage the C-Pulse therapy.

After implantation of the C-Pulse System, patients will be followed up for 5 years to collect performance and safety data.

The estimated time course of the study is as follows:

First Patient In: May 2013

Last Patient In: Dec 2014

Last Patient Out: Dec 2019

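### Section 5.3 times the exclusions to enrollment, so for patients consented after implant a post-implant systemic infection or aortic dissection can exclude them; the follow-up clock is also contradictory

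*Combined protocol and SAP*

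**What the plan says.** **Entry after implant.** Section 5.2, like the synopsis and section 4.1, lets patients be enrolled "retrospectively with informed consent for the collection of the patient's data obtained after the procedure". Sections 5.4 and 9.1 require consent before enrollment, so these patients are enrolled after the device is in.

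**Items timed to enrollment.**
- The whole exclusion list in 5.3: "Patients with the following conditions (contraindications in the IFU), as assessed within 90 days prior to enrollment, have to be excluded". It includes any history of aortic dissection (item 4) and active systemic infection (item 11).
- The CRT timing in 5.2: "When clinically indicated, CRT should be implanted ≥ 90 days prior to enrollment".
- The liver-enzyme item in 5.5 (30 days).

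Section 5.4 adds: "The investigator(s) will verify each patient's inclusion/exclusion criteria before inclusion in the study".

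**Items timed to implantation.** In 5.5 these are the six-minute walk (30 days), cardiac surgery (90 days), creatinine or dialysis (30 days) and stroke or TIA (30 days). Table 3 marks eligibility only in its pre-implant column, and its footnote 3 counts a 90-day imaging allowance back from implant.

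**Follow-up clock.** Section 5.6: "The data will be recorded from baseline and during a 5 year follow-up period following the enrollment". Section 6.2: "After implantation of the C-Pulse System, patients will be followed up for 5 years to collect performance and safety data". Footnote 1 to Table 3 and the secondary endpoints in 6.3 are timed from implant.

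**The concern.** For a patient consented before implant, the choice between enrollment and implantation as anchor matters little. For a patient consented afterwards, it decides whether eligibility is judged on the state before treatment or on a state that treatment may have caused. Under the wording of 5.3, the second reading is possible, and two exclusions then overlap with events that the study is meant to count. Exclusion would depend on outcome, and the affected safety rates would be too low. A confidence interval around those rates would not show it, because the patients concerned never enter the denominator.

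This is distinct from losing patients who die before they can consent. The patients at issue here are alive and have agreed to take part.

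The clock matters for a related reason. Event rates and five-year status need one time zero, and for patients consented after implant the two stated clocks end on different dates.

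**Working it through.** The documents state no figure on this point. N = 50 in section 6.6 is a chosen size with a precision check whose table is not in the available text, so there is nothing to reproduce.

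**1. Where the 5.3 window falls.** Let implant be day 0 and enrollment day d. The window runs from day d − 90 to day d, so the share after implant is min(d, 90)/90. The documents give no consent lag; the values of d are assumed.
- d = 30: day −60 to day 30, so 30/90, one third, is post-implant.
- d = 60: 60/90, two thirds.
- d = 90 or more: all of it. For d above 90, a pre-implant assessment lies outside the stated window altogether.

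**2. Which exclusions overlap with counted events.**
- Active systemic infection (5.3 item 11) overlaps with sepsis, defined in 8.2.4 as systemic involvement by infection. Sepsis is counted under the protocol-defined adverse events in 6.4.
- Any history of aortic dissection (item 4) overlaps with aortic disruption, defined in 8.2.4 as an intimal disruption of the ascending aorta and named as a primary safety endpoint in 6.4. The terms overlap but are not identical.
- Exit-site infection, at 40% the figure that section 4.3 gives for the premarket study, is not an exclusion unless it becomes systemic.

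**3. Size of the bias, by illustration.** Let p be the true event rate, f the share of patients entered retrospectively, and q the probability that a retrospective patient with the event is excluded by it. Here q also covers whether the event occurs before consent. Excluded patients leave both numerator and denominator:

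observed rate = p(1 − fq) / (1 − pfq)

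The documents give neither f nor q. For p I use 5%, the order of the single premarket case in section 4.3 (1/20, a sternal wound infection that ended in aortic disruption; exact 95% interval 0.1% to 24.9%). The chance of seeing at least one event in 50 is 1 − (1 − observed rate)^50.

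| f | q | Observed rate when p = 5% | P(at least one in 50) |
|---|---|---|---|
| any | 0 (pre-implant rule) | 5.0% | 92.3% |
| 0.25 | 0.25 | 0.046875/0.996875 = 4.7% | 91.0% |
| 0.5 | 0.5 | 0.0375/0.9875 = 3.8% | 85.6% |
| 0.5 | 1 | 0.025/0.975 = 2.6% | 72.7% |

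For scale, 3 events in 50 (6%) have an exact 95% interval of 1.3% to 16.6%, about 15 points wide. The last two rows lose 1.2 and 2.4 points. That is smaller than the interval, but it is systematic.

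**4. The clock.** With assumed lags of 3, 6 and 12 months from implant to enrollment, five years from enrollment ends at month 63, 66 and 72 after implant (60 + lag). Five years from implant always ends at month 60, which leaves 57, 54 and 48 months after enrollment.

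**The case against.** The strongest reply is that the intended reading is plain. Section 5.5 applies the criteria to patients eligible for implantation, 5.3 calls the exclusions contraindications, Table 3 places eligibility before implant, and the synopsis list carries no enrollment window. On that view, the word enrollment in 5.3 is loose drafting. As evidence of intent this stands. It does not remove the problem. Section 5.3 is an explicit mandatory rule, section 6.2 applies the same criteria to eligibility for the study, section 5.4 checks them before inclusion in the study, and no sentence confines patients consented after implant to their pre-implant status. The passages conflict, and none overrides the others.

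The study is also single-arm and descriptive, with no hypothesis test, so no formal conclusion turns on the bias. That limits the weight of the point.

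A reader might infer more than the documents support:
- **That all eligibility windows run from enrollment.** They do not; most other dated items in 5.5 run from implantation.
- **That follow-up runs from enrollment.** Sections 5.6 and 6.2 disagree, and the visit schedule is post-implant.
- **That most device complications would exclude.** Exit-site infection alone does not. The premarket sternal and pneumo-mediastinum infections (5% each) are not listed exclusions and are not described as systemic, so pooling them into a 10% rate of excluding events is unsupported. Item 6 concerns root replacement, not repair. Systolic pressure below 90 mmHg is neither a listed safety endpoint nor a named adverse event.
- **That a CRT effect would be credited to the device.** Counted from enrollment, CRT placed on the day of cuff implant could meet the 90 days, but the criterion also requires non-response to CRT, which same-day placement cannot establish.
- **That results as a whole would look too good.** NYHA class has no stated window. If it were judged at enrollment, patients who improved after implant would fail inclusion, which works in the other direction.

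**Conclusion.** The point holds in this form. For patients consented after implant, the enrollment anchor in 5.3 lets a post-implant active systemic infection or aortic dissection exclude a living, consenting patient. This would bias the sepsis and aortic disruption rates downward, and it conflicts with section 5.5 and Table 3. The direction for those two events follows from the text. The size does not: it depends on the retrospective share, the consent lag and how literally sites apply 5.3, none of which is stated. The fall from 5% to between 3.8% and 2.6% rests on half the patients being retrospective and 50% to 100% of those with the event being excluded by it; if few are retrospective, or sites already use pre-implant records, the effect is close to nil. The follow-up clock is a separate and certain contradiction between 5.6 and 6.2, whose effect is limited to patients enrolled at a later date than their implant.

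**What to change.** - In 5.3, and for the other items timed to enrollment (CRT in 5.2, liver enzymes in 5.5), state that for patients consented after implant eligibility is judged only from records dated before implantation, and that no post-implant finding may exclude a patient from the study.
- Reconcile the enrollment and implantation anchors in 5.2 and 5.5 with each other and with Table 3.
- Reconcile 5.6 with 6.2 so that follow-up and event rates use one time zero, consistent with the post-implant visit schedule.

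The cost is a wording amendment and one e-CRF check of each eligibility date against the implant date. No visits or patients are added. Complication rates may look slightly less favourable. The change does not address patients who die before they can consent; reporting all implanted patients at each site, with reasons for non-enrollment, would at least make that loss visible.
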